This hypothesis will be tested using a one sided one sample test of proportions with the normal approximation, at the 5% significance level. We will also report a 95% confidence interval for the true proportion of subjects who experience a 'success' as with a sample size of 25 patients, we will have a margin of error of 0.19. In the experimental treatment phase, patients who either experience treatment failure (as previously defined on pg. 22) or clinical deterioration (as defined above on pg. 22) will be withdrawn before Week 12 and we will therefore impute for both non-positive responses at Week 12, a discrete QMG score increase of more than 3 points. For example, if the largest deterioration score observed is 8, then a QMG score ranging between 4 and 8 will be imputed at Week 12. Although we do not expect many missing observations at Week 12 of the SCIg phase, the outcomes recorded at these intermediate time points will allow us the ability to impute data at this endpoint. Specifically, in the case where no outcome is available for a subject at Week 12 due to the subject's perception of a worsened condition, we will impute for this subject a QMG score increase at Week 12 of more than 3 points. In cases where subjects refuse to proceed to Week 12 or are lost to follow-up even though they were responding well on the treatment (as evidenced by the intermediate measurements), we will impute their Week 12 observation using the last observation carried forward (LOCF) approach. We will complement our LOCF approach with sensitivity analyses covering the following alternate approaches: (1) Multiple imputation with 5 replicates per imputation to account for the uncertainty inherent to the imputation (2) Mixed model calculations accounting for the trend in QMG values over time (3) Best case and worst-case scenarios.

2. Additional Exploratory Analysis of Primary Outcomes:

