Analysis of secondary outcome measures as listed in the Aims section such as MG-ADL, MG QOL-15, the MG composite score and TSQM will primarily be conducted only for those who complete the study. We will conduct a two-sided signed-rank test to assess whether these scores changed significantly from baseline (Week 0) to Week 12. In case of missing values for the MG-ADL, MG QOL-15, and the MG composite score in cases where subjects refuse to proceed to Week 12 even though they were responding well on the treatment (as evidenced by the intermediate measurements) or are lost to follow-up, we will impute their Week 12 observation using the last observation carried forward (LOCF) approach. We will also report the proportion of subjects enrolled in the subcutaneous experimental treatment study phase (Week 0 to Week 12) fulfilling our definition of improvement (as mentioned on pg. 24) along with a 95% confidence interval. We will compare between the two phases the percent of subjects meeting the definition of deterioration, worsening, stability and improvement. We will analyze the effect of prednisone dosage (Increase vs Not Increased) on clinical improvement (Yes vs No) using a 2x2 Fisher's exact test in the SCIg phase of the study by comparing dose levels at Week 12 to Week 0 for those patients who complete Week 12 of the study. To do this, we will ask the patients at Week 0, Week 4, Week 8 and Week 12 about their prednisone dosage levels. Those patients who exit the study prematurely due to deterioration before Week 12 will be excluded from this Fisher's test calculations. In the event that the Week 12 prednisone dose observation is missing even when patients have completed Week 12 (QMG or MGADL done), we will use the LOCF approach to impute this missing value as long as at the last available assessment, the patient was deemed to be improving (in terms of QMG or MGADL scores as defined under "Subject deterioration, worsening, rescue medication and improvement"). A two-sided signed-rank test will be also conducted to assess whether IgG levels changed significantly between the intravenous screening phase (Week -10 to Week 0) to the subcutaneous experimental treatment study phase (Week 1 to Week 12). All tests will be conducted at the 5% level of significance. For the secondary outcome measures related to monitoring the safety profile of patients between the two study phases, a similar test will be conducted when the safety parameters measured are continuous variables and a one sample test for the difference in proportions will be conducted when they are measured as treatment-related severity rates. The comparison epochs for safety are also between the intravenous screening phase (Week -10 to Week 0) and the subcutaneous experimental treatment study phase (Week 0 [after first SCIg dose] to Week 12). Adverse events occurring in the two phases (mild, moderate/severe) will be summarized using a McNemar's test.

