
4. Sample Size Considerations:

With a sample size of 25 patients, we have at least 70% power to detect a success rate of 85% or higher using the chi-square test compared to an expected success rate of 65% or lower. We anticipate we will be able to assess efficacy, safety and tolerability of SCIg with the current sample size over 12 weeks and compare that these parameters to the 12-week IVIg phase. The selected sample size will enable us to complete study enrollment with the current number of sites.

MG is a rare disease and MG studies have consistently experienced difficulty enrolling subjects due to a multiplicity of poorly understood reasons.³⁴ In the Methotrexate study of MG and similar to other previous MG studies, enrollment has been a challenge. However, we managed to complete enrollment of 50 subjects by adding sites. In the current SCIg study protocol, the eligible

study population is narrowed due to the inclusion criterion requiring MG cases to be on stable IVIg doses. While 85 to 90% of MG patients are seropositive for either the AchR or MuSK autoantibodies, some of these cases are treated in clinical practice with IVIg maintenance. Based on the pre-site selection feasibility survey, 25 subjects is a reasonable and achievable goal with the selected five sites. If enrollment is found to be slower than predicted, we are ready to add more sites to complete this study.

5. Study Populations:

Safety population: All patients enrolled at baseline constitute the safety population. The subjects in this population will be included in the analysis of adverse events, vital signs, clinical laboratory findings, and other safety data. But for the purpose of statistical analyses, the rates of adverse events experienced by these subjects in the SCIg phase will be compared to the rates experienced during the IVIg phase of the study. Adverse events will be tabulated by treatment group, severity, and perceived relationship to study drug. For each adverse event, the treatment groups will be compared regarding the occurrence of at least one event using the Fisher's exact test. The comparisons will be repeated excluding all mild symptoms. Continuous measures such as vital signs and laboratory test results will be analyzed in a manner similar to that for the primary outcome variable.

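### The SAP promises to compare adverse event rates between phases, but defines no rate and names only yes/no tests, so repeated events are never counted in a test

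*SAP*

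**What the plan says.** Section 5 (Safety population) states the aim: "the rates of adverse events experienced by these subjects in the SCIg phase will be compared to the rates experienced during the IVIg phase". It does not say whether a rate means events per patient, events per week or the share of patients affected, and it attaches no test to that sentence. It then plans tabulation by group, severity and relationship. For each adverse event, the groups "will be compared regarding the occurrence of at least one event" by Fisher's exact test, and this is repeated without mild events.

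Section 3 adds McNemar's test by severity, and a one-sample test for a difference in proportions for treatment-related severity rates. For other safety variables, "a similar test will be conducted when the safety parameters measured are continuous variables", which in context means the signed-rank test. It sets the safety epochs as Week -10 to Week 0 (IVIg) and Week 0 after the first SCIg dose to Week 12 (SCIg), and adds "All tests will be conducted at the 5% level of significance".

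Under unscheduled visits, Section 5 also plans to compare between phases the rates of visits caused by side effects, again without naming a method.

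**The concern.** A rate comparison is announced, and the tests supplied cannot carry it. Each reduces a patient's experience in a phase to any event or none. A patient with one headache on IVIg and ten on SCIg counts as affected in both phases and shows no difference. Once most patients have had one event of any kind, the yes/no measure has little room to move, however much the burden grows.

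Section 4 expects the trial to assess safety and tolerability of SCIg and to compare them with the IVIg phase. If the only tests reported are yes/no, a clearly higher event burden after the switch could be reported as no difference. This is separate from whether the test is paired and from the unequal epochs: the loss remains with a paired test and equal phases.

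**Working it through.** **The plan's own figure.** The SAP states no power or event rate for adverse events. Its only power statement is for the primary outcome: "With a sample size of 25 patients, we have at least 70% power to detect a success rate of 85% or higher", against a null of 65%, by a "one sided one sample test of proportions with the normal approximation, at the 5% significance level". With the null variance for the critical value and the alternative variance for power:

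z = (0.85 − 0.65 − 1.645·√(0.65·0.35/25)) / √(0.85·0.15/25) = (0.20 − 0.157)/0.0714 = 0.603, so power is 72.7%.

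The statement reproduces (68.2% by exact calculation). It says nothing about safety.

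**Inputs for the adverse event check.**
- From the SAP: 25 patients, each observed in both phases; 5% level; epochs of 10 and 12 weeks (Section 3).
- Assumed: a mean of m events per patient on IVIg, and a doubled weekly rate on SCIg. Counts are Poisson, with a gamma patient effect shared by both phases (mean 1, variance v of 0.5 to 1). Tests are two-sided, because the SAP does not state sidedness for adverse events.

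**Saturation.** The share of patients with at least one event is 1 − (1 + v·m)^(−1/v), or 1 − e^(−m) without a patient effect. For 2 versus 4 events:
- no patient effect: 1 − e^(−2) = 86% versus 1 − e^(−4) = 98%
- v = 0.5: 1 − 2^(−2) = 75% versus 1 − 3^(−2) = 89%
- v = 1: 1 − 1/3 = 67% versus 1 − 1/5 = 80%

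Events double while the yes/no share moves by 12 to 14 points.

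**Power for a doubling, equal phases, v from 0.5 to 1 (simulated):**

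| Events, IVIg vs SCIg | Fisher | McNemar exact | McNemar asymptotic | Signed-rank on counts |
|---|---|---|---|---|
| 1 vs 2 | 11–18% | 18–24% | 28–33% | 75–76% |
| 2 vs 4 | 6–12% | 12–14% | 25–29% | 94–96% |
| 3 vs 6 | 4–5% | 5–6% | 21% | 98–99% |

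Repeat simulations agree within simulation error; across them the signed-rank range is about 74–99%. The signed-rank type I error is 4–5%. The one-sample test for a difference in proportions was not simulated; it too uses only the yes/no data.

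**Stated epochs.** With 10 and 12 weeks, equal weekly rates already give 12/10 = 1.2 times as many events on SCIg, and a doubled weekly rate gives 2 × 1.2 = 2.4 times. At 1 to 3 events on IVIg, Fisher and exact McNemar then reach about 7–37%. A further run for this note (3,000 trials per setting) gave 28–49% for asymptotic McNemar. Part of that gain is longer observation, not a higher weekly rate. Signed-rank on events per week keeps about 74–99%.

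**Sparse events.** At 0.25 versus 0.5 in equal phases, Fisher has 8–12%, exact McNemar 12–15% and signed-rank 24–26%. With the 10- and 12-week epochs the signed-rank advantage at this rate largely disappears: about 19–21%, against 19–23% for exact McNemar, in the same further run.

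**Error of the weekly-rate comparison.** With equal weekly rates over 10 and 12 weeks, the signed-rank error is about 5–6% from 1 event upward. It rises to about 6–8% at 0.25 to 0.5 events.

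**The case against.** The strongest reply is that the plan does not ignore rates. Section 5 says they will be compared, Section 3 gives a test for continuous safety variables that could take a per-patient event rate, and unscheduled visits due to side effects are to be compared as rates. A reader might infer that adverse events are tested only as ever/never by design. The document does not support that: a rate comparison is intended, and what is missing is its definition and method. The reply does not close the gap, however. The SAP never lists event rates among the continuous safety variables (Section 5's examples are vital signs and laboratory results).

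Second, Fisher's test is run for each event type, whereas the large power differences above belong to pooled events. A reader might infer that a doubling would be missed because the endpoint is yes/no. For a single type at about 0.25 events per patient or less, a count test usually misses it too, because 25 patients yield too few events. Nor is a miss certain with pooled events: with no patient heterogeneity and 0.5 to 1 event on IVIg, Fisher reached about 55% with the stated epochs. This objection stands and limits the point.

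Third, the share of patients with at least one event is a conventional safety summary. The SAP claims no power for safety, and says nothing on how often reactions recur. It therefore cannot be said that recurrence carries most of the tolerability signal, or that a count analysis must become the main one. This stands too.

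**Conclusion.** The point holds in a limited form. The SAP promises a comparison of adverse event rates, leaves the rate undefined, and names no test that uses event counts. For pooled events the cost can be large: with 1 to 3 events per patient on IVIg and a patient-effect variance of 0.5 to 1, yes/no tests detect a doubling far less often than a paired count comparison, whichever form of McNemar is used. The size rests on these assumed rates and heterogeneity, since the SAP gives neither. For sparse single event types the gain is small or nil. The primary efficacy analysis is untouched. This is a cheap and worthwhile improvement to the safety analysis; the existing tests are not invalid on this ground.

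**What to change.** Keep the per-type ever/never analyses. Add to Section 5, as the method for the rate comparison it already promises:

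- Define the rate as a patient's number of adverse events divided by weeks of actual exposure in that phase, so that early withdrawals and unequal epochs are handled. Include patients with exposure in both phases.
- Compare it within patient by the signed-rank test, named explicitly, and report the median paired difference. Do this for all events and for moderate/severe events.
- As a check, fit a Poisson or negative binomial model with a patient effect and a log-exposure offset, because the signed-rank error is mildly inflated when events are sparse.
- State one rule for counting repeat and continuing episodes, applied identically in both phases.
- Settle the IVIg period used as the denominator: the SAP describes that phase as 9 weeks (Section 1), Week -10 to Week 0 (Section 3) and 12 weeks (Section 4), and these must be reconciled.

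The cost is a short SAP paragraph and a few lines of SAS, using adverse event records the plan already tabulates. The real downside is the counting rule, because a count analysis is only as good as its consistency. The addition need not replace the existing tests as the main adverse event analysis.
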